### **9.6.3. Demographic and Baseline Characteristics**

Demographic and baseline characteristics will be summarized using descriptive statistics for all patients who receive TEGSEDI. All patients enrolled will be included in a summary of patient disposition.

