## **9.8. Limitations of the Research Methods**

Patient-selection bias is a consideration, as motivation to consent to join the study can vary between patients for different reasons. If prescribers and patients are not willing to participate, selection bias may occur, resulting in limited generalizability of the results. However, as TEGSEDI ordering and dispensing data will be available to the Sponsor, all patients who will receive TEGSEDI treatment will be known at the sites selected to participate in this study. All eligible patients at the study sites who have received less than 9 doses will be invited to participate minimizing the selection bias.

Patients may be enrolled in the study if they have initiated treatment with commercial TEGSEDI prior to study enrollment and received less than 9 doses. This approach allows patients who began treatment prior to the launch of the study to be included in order to evaluate as large an exposure population as possible. The limitation of this approach is that patients who initiate TEGSEDI and discontinue shortly thereafter may not be included and could differ in demographic characteristics from those who become enrolled, i.e., survivor bias. Also, any AESI that occur shortly after treatment initiation may be underrepresented in the study population. Another limitation of this approach is that patients will have had TEGSEDI treatment prior to their baseline testing; therefore, it will not be possible to evaluate the change in test results from one study visit compared to prior to receiving the patient's initial dose of TEGSEDI.

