### 8.1 Analysis Populations

The safety set includes all patients who received at least one dose of TEGSEDI while enrolled in this study protocol. The safety set will be used in the summary of demographics, medical history, patient disposition, AEs, concomitant medications and ADA (Anti-drug antibody).

The evaluable set includes patients in the safety set having at least one post-dose assessment. The evaluable set will be used in the summaries of AEs by study visit and vital signs and cytokines/inflammatory markers recorded over a 24-hour period.

Listings will be run on the safety set.

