### 8.2 Description of Statistical Analyses

#### 8.2.1 Enrollment Disposition and Baseline Information

Summaries using descriptive statistics using the safety set will be provided for:

- Patient disposition

 	
Title: Statistical Analysis Plan
 
Program Name: "A Phase 4 Safety Study Assessing the Adverse Events Occurring Within 24 Hours of TEGSEDI Administration in Patients with polyneuropathy of Hereditary Transthyretin-mediated Amyloidosis (hATTR-PN)"
 
Protocol #: TEG4004
 
[REDACTED]
 
Version: Final 2.0 Effective Date: 06 October 2023

--	---

- Demographics and other baseline characteristics
- Medical history

Patient disposition will be presented by counts and percentages for the completion and discontinuation of the study treatment and for completion of the post-treatment follow-up phase. Medical history will be coded starting with MedDRA (Medical Dictionary for Regulatory Activities) version 22.1 or higher and coding will be re-run periodically using the most recent version of MedDRA. Medical history will be summarized by System Organ Class (SOC) and Preferred Term (PT).

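### Protocol v2.0 puts patient disposition on all enrolled patients; the SAP puts it, and every listing, on dosed patients only, so anyone enrolled but never dosed drops out of both

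*Combined protocol and SAP*

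**What the plan says.** Protocol v2.0, section 9.6.3, names two populations in consecutive sentences. For demographics: "Demographic and baseline characteristics will be summarized using descriptive statistics for all patients who receive TEGSEDI". For disposition: "All patients enrolled will be included in a summary of patient disposition". The second is the wider of the two.

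The SAP (Final 2.0, 06 October 2023) uses one population for both. Section 8.1 defines it: "The safety set includes all patients who received at least one dose of TEGSEDI while enrolled in this study protocol". It then assigns it: "The safety set will be used in the summary of demographics, medical history, patient disposition, AEs, concomitant medications and ADA". Section 8.2.1 repeats the assignment, with patient disposition as the first item under the line "Summaries using descriptive statistics using the safety set will be provided for". On the content of the table, 8.2.1 says: "Patient disposition will be presented by counts and percentages for the completion and discontinuation of the study treatment", together with completion of post-treatment follow-up. It describes no row for patients enrolled but not dosed. Section 8.1 closes with "Listings will be run on the safety set".

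The SAP defines a safety set and an evaluable set. It defines no enrolled set and does not explain the narrower basis for disposition.

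**The concern.** A disposition table accounts for everyone who entered the study. If its population starts at the first dose, the step from enrolled to dosed cannot be seen: nobody can be lost before dosing, by construction. Completion percentages are also taken on a smaller denominator than the protocol intended.

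The listings matter as well. Under protocol 11.4.1 and 11.4.2, serious and non-serious events are collected from signature of the consent form. An event in a patient who consents, enrols and leaves before any dose would be in the database but in none of the SAP's AE listings. For a safety study this is a gap in accounting, even though such an event is not treatment-emergent under SAP 8.2.2.1.

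**Working it through.** **The plan's own figure.** The only number nearby is the sample size statement in protocol 9.4: 75 patients give 95% probability of detecting an AE with 4% incidence. The exact binomial gives 1 − 0.96^75 = 0.953, so it reproduces. It is not in dispute. The point here is about populations and was checked by comparing the texts.

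**Step 1: do the populations differ?**

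| Output | Protocol v2.0, 9.6.3 | SAP 8.1 and 8.2.1 |
|---|---|---|
| Demographics | Patients who receive TEGSEDI | Safety set |
| Disposition | All enrolled | Safety set |
| Listings | Not specified there | Safety set |

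Demographics agree in substance. Disposition does not.

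**Step 2: can a patient be enrolled without a dose?** The analysis sections do not define enrolment, but the texts treat it as separate from dosing. Protocol 9.2.2.1.1 collects demographics on all enrolled patients as part of screening. The SAP's safety set definition asks for a dose while enrolled, a condition that would add little if enrolment already required a dose. SAP 6 defines a screening period running from consent to the first on-study dose, and SAP Table 1 allows it up to 2 weeks. So the category can exist. It may also be empty, because a footnote to Table 1 in both documents allows screening and Month 0 on the same day.

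**Step 3: size.** Let N be the number enrolled and k the number enrolled but never dosed. The safety-set table has denominator N − k and omits k/N. The documents do not give k. Take N = 75 (the plan says at least 75) and, as an assumption, k from 0 to 6. To show the effect on a percentage, assume also that 60 patients complete, which is 60/75 = 80.0% of those enrolled.

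| k (assumed) | Denominator 75 − k | Omitted, k/75 | Completion, 60/(75 − k) |
|---|---|---|---|
| 0 | 75 | 0% | 80.0% |
| 2 | 73 | 2.7% | 82.2% |
| 5 | 70 | 6.7% | 85.7% |
| 6 | 69 | 8.0% | 87.0% |

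**Step 4: do AE rates change?** No. SAP 8.2.2.2 divides by patients dosed at the visit, or by the evaluable set for the overall rate. Undosed patients belong in neither.

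**Step 5: is safety set membership itself clear?** Not entirely. Patients already taking the drug may enrol, and dosing is weekly, so a home dose can fall between consent and Month 0. Read literally, SAP 8.1 would admit an enrolled patient with only such a dose. SAP 6 and 8.2.5 start the treatment period and exposure at the first on-study or on-site injection, which that patient never had. The SAP does not say which reading governs.

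**The case against.** Five objections carry weight.

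- **Protocol version.** SAP 2 says it implements protocol version 3.0 of 23 May 2023; the protocol supplied is v2.0. The SAP reflects other changes, such as dropping the nine-dose limit on prior treatment, so 9.6.3 may have changed too. This stands. A departure from the governing protocol cannot be asserted until v3.0 is checked. If v3.0 did narrow the population, the gap in accounting for enrolled patients would remain.
- **Other outputs.** A reader might infer that undosed patients would appear nowhere. The documents do not support that. SAP 9 lists recruitment status separately from disposition in the annual reports, protocol 9.6.4 calls for narratives of all discontinuations, and the mock tables are in an appendix that was not available. The point covers the disposition summary and listings as the SAP text specifies them.
- **Survivor bias.** A reader might link this to protocol 9.8, which warns that "patients who initiate TEGSEDI and discontinue shortly thereafter may not be included", and conclude that a corrected table would measure that bias. It would not. Section 9.8 describes patients who stop before joining the study or who decline to join. Neither group is enrolled.
- **The home-dose patient.** It is tempting to illustrate the loss with a patient who reacts to a home dose during screening and leaves. If that patient was already enrolled, the literal SAP definition may keep them in the safety set. The example shows an ambiguity to settle and does not prove a loss.
- **Size.** No figure in the documents supports any particular number of undosed patients, and zero is plausible. This also stands.

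**Conclusion.** The point holds as a reporting correction. Protocol v2.0 and the SAP name different populations for disposition. Following the SAP removes any enrolled but undosed patient from the numerator and denominator of the disposition table and from all listings, including any AE or SAE recorded for that patient after consent. With 75 enrolled and 0 to 6 undosed, both assumed, 0% to 8.0% of enrolled patients are omitted. If 60 complete (also assumed), the completion rate reads 80.0% to 87.0% where the figure for enrolled patients is 80.0%. The true effect may be nil. No AE incidence estimate or confidence interval changes.

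The conclusion rests on v3.0 having kept the v2.0 wording of 9.6.3, and on enrolment preceding the first dose, which the texts imply but do not define.

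**What to change.** Check protocol v3.0, section 9.6.3, first. Then, in the SAP:

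1. Define an enrolled set in 8.1.
2. In 8.1 and 8.2.1, base the disposition table and its listing on the enrolled set. Add rows for enrolled, dosed on study (safety set) and evaluable, and give the reason for not being dosed.
3. Run the listings of all AEs and of SAEs on the enrolled set.
4. State in 8.1 whether a home dose taken after consent but before Month 0 counts toward the safety set.
5. Keep the safety set for the other tables that now use it.

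The cost is a few sentences in the SAP, a few extra table rows and a change of population flag for the listings. Protocol 9.2.4.5 already requires the reason for study withdrawal in the eCRF, so reasons for leaving before dosing should need little or no new data collection. No other analysis changes.

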### **9.6.4. Safety Analysis**

Patient incidence rates of all AEs will be tabulated by Medical Dictionary for Regulatory Activities (MedDRA) system organ class (SOC), and by MedDRA preferred term (PT). Narratives of deaths, all discontinuations, serious AEs, pregnancies and AEs of special interest (AESI) will also be provided.

All treatment emergent AEs, all treatment emergent AEs potentially related to TEGSEDI, all treatment emergent serious AEs, and all treatment emergent serious AEs potentially related to TEGSEDI will be summarized.

Incidence (95% confidence interval) of AEs occurring within 1 day of TEGSEDI administration, and time to onset from TEGSEDI injection and duration of these AEs will be summarized by visit and overall in any visit. The rates of AEs during the 1-day visit occurring after preventive measures will also be summarized. Resolution time with and without treatment administered for the AEs will be summarized.

For each study visit on treatment, the result and change from pre-dose baseline in vital signs (body temperature, heart rate, respiratory rate, and systolic, diastolic blood pressure) and cytokines/inflammatory markers will be summarized using descriptive statistics for all patients in the Evaluable Set and by presence/absence of AEs within 1 day of TEGSEDI administration.

### **9.6.5. Interim Analyses and Early Stopping Guidelines**

No formal interim analysis is planned; although data related to disposition, exposure, and safety considerations will be reported on an annual basis.

## **9.7. Quality Control**

### **9.7.1. Monitoring**

The Sponsor representative and regulatory authority inspectors are responsible for contacting and visiting the investigator for the purpose of inspecting the facilities and, upon request, inspecting the various records of the trial (e.g., eCRFs and other pertinent data) provided that patient confidentiality is respected.

The Sponsor monitor or designee is responsible for inspecting the eCRFs at regular intervals throughout the study to verify adherence to the protocol; completeness, accuracy, and consistency of the data; and adherence to local regulations on the conduct of clinical research. The monitor should have access to patient medical records and other study-related records needed to verify the entries on the eCRFs.

The investigator agrees to cooperate with the monitor to ensure that any problems detected in the course of these monitoring visits, including delays in completing eCRFs, are resolved.

To ensure the quality of clinical data a clinical data management review will be performed on patient data received by the Sponsor or designee. During this review, patient data will be checked for consistency, omissions, and any apparent discrepancies. In addition, the data will be reviewed for adherence to the protocol and GCP. To resolve any questions arising from the clinical data management review process, data queries and/or study center notifications will be sent to the study center for completion and return to Sponsor or designee.

The investigator will sign and date the indicated places on the case report form. These signatures will indicate that the investigator inspected or reviewed the data on the case report form, the data queries, and the study center notifications, and agrees with the content.

#### **9.7.2. Language**

E-CRFs must be completed in English. Generic names and trade names are acceptable for concomitant medications. Combination medications should be recorded using their trade name.

All written information and other material to be used by patients and investigative staff must use vocabulary and language that are clearly understood.

#### **9.7.3. Inspection and Auditing Procedures**

In accordance with ICH GCP and the Sponsor's audit plans, this study may be selected for audit by representatives from the Sponsor's Clinical Quality Assurance Department (or designees). Inspection of study center facilities (e.g., pharmacy, drug storage areas, laboratories) and review of study-related records will occur to evaluate the trial conduct and compliance with the protocol, ICH GCP, and applicable regulatory requirements.

#### **9.7.4. Source Document Maintenance**

Source documents contain the results of original observations and activities of a clinical investigation. Source documents include, but are not limited to, medical records (progress notes), computer printouts, screening logs, and recorded data from automated instruments.

All source documents from this study will be maintained by the site and made available for inspection by authorized persons. The original signed ICF for each patient shall be filed with records kept by the site and a copy shall be given to the patient.

#### **9.7.5. Record Maintenance**

Records will be retained in accordance with the applicable local regulations. All essential study documents, including records of patients, source documents, signed ICFs, and eCRFs, must be kept by the investigator for at least 15 years from study termination/completion or until instructed in writing by the Sponsor that records may be destroyed or forwarded to the Sponsor. The Investigator shall take responsibility for maintaining adequate and accurate hard copy source documents of all observations

and data generated during this study. Such documentation is subject to inspection by the Sponsor, its representatives, and regulatory authorities.

If an investigator moves, withdraws from the study, or retires, the responsibility for maintaining the records must be transferred to another person who will accept responsibility. Notice of transfer must be made to and agreed by the Sponsor.

## **9.8. Limitations of the Research Methods**

Patient-selection bias is a consideration, as motivation to consent to join the study can vary between patients for different reasons. If prescribers and patients are not willing to participate, selection bias may occur, resulting in limited generalizability of the results. However, as TEGSEDI ordering and dispensing data will be available to the Sponsor, all patients who will receive TEGSEDI treatment will be known at the sites selected to participate in this study. All eligible patients at the study sites who have received less than 9 doses will be invited to participate minimizing the selection bias.

Patients may be enrolled in the study if they have initiated treatment with commercial TEGSEDI prior to study enrollment and received less than 9 doses. This approach allows patients who began treatment prior to the launch of the study to be included in order to evaluate as large an exposure population as possible. The limitation of this approach is that patients who initiate TEGSEDI and discontinue shortly thereafter may not be included and could differ in demographic characteristics from those who become enrolled, i.e., survivor bias. Also, any AESI that occur shortly after treatment initiation may be underrepresented in the study population. Another limitation of this approach is that patients will have had TEGSEDI treatment prior to their baseline testing; therefore, it will not be possible to evaluate the change in test results from one study visit compared to prior to receiving the patient's initial dose of TEGSEDI.

## **9.9. Other Aspects**

### **9.9.1. Protocol Amendments**

Protocol amendments must be made only with the prior approval of the Sponsor or designee. Agreement from the investigator must be obtained for all protocol amendments and amendments to the informed consent document. The regulatory authority and IEC/IRB must be informed of all amendments and give approval for any amendments likely to affect the safety of the patients or the conduct of the trial. The investigators **must** send a copy of the approval letter from the IEC/IRB to the Sponsor or designee.

### **9.9.2. Compensation for Injury**

The Sponsor maintains appropriate insurance coverage for clinical trials and will follow applicable local compensation laws. Patients will be treated and/or compensated for any study-related illness/injury in accordance with the information provided in the Compensation for Injury section of the Informed Consent document.

## 10. Protection of Human Patients

### 10.1. Informed Consent

The written informed consent document should be prepared in the language(s) of the potential patient population, based on an English version provided by the Sponsor or designee.

Before a patient's participation in the trial, the investigator is responsible for obtaining written informed consent from the patient or legally acceptable representative after adequate explanation of the aims, methods, anticipated benefits, and potential hazards of the study before any data are collected for the study. The patient or legally acceptable representative must be given sufficient time to consider whether to participate in the study.

The acquisition of informed consent and the patient's agreement or refusal to notify his/her primary care physician should be documented in the patient's medical records and the ICF should be signed and personally dated by the patient or a legally acceptable representative and by the person who conducted the informed consent discussion (not necessarily the investigator). The original signed ICF should be retained in the Investigator Site File and in any other locations required by institutional policy, and a copy of the signed consent form should be provided to the patient or legally acceptable representative.

### 10.2. Ethical Conduct of the Study

All applicable regulations and guidelines of current GCP as well as the demands of national drug and data protection laws and other applicable regulatory requirements must be followed.

### 10.3. Independent Ethics Committee/Institutional Review Board

A copy of the protocol, proposed ICFs, other written patient information, and any proposed advertising material must be submitted to the IEC/IRB for written approval. A copy of the written approval of the protocol and ICF must be received by the Sponsor or designee before recruitment of patients into the study. A copy of the written approval of any other items/materials that must be approved by the study center or IEC/IRB must also be received by the Sponsor or designee before recruitment of patients into the study.

The investigator must submit to and, where necessary, obtain approval from the IEC/IRB for all subsequent protocol amendments and changes to the informed consent document. The investigator should notify the IEC/IRB of deviations from the protocol in accordance with ICH GCP. The investigator should also notify the IEC/IRB of Serious Adverse Events (SAEs) occurring at the study center and other AE reports received from the Sponsor or designee, in accordance with local procedures.

The investigator will be responsible for obtaining annual IEC/IRB approval/renewal throughout the duration of the study.

### 10.4. Patient Confidentiality

The investigator must ensure that the patient's confidentiality is maintained. On the eCRFs or other documents submitted to the Sponsor or designee, patients should be identified by initials (if permitted by local law) and a patient identification number only. Documents that are not for submission to the Sponsor or designee (e.g., signed ICFs) should be kept in strict confidence by the investigator.

In compliance with Federal and local regulations/ICH GCP Guidelines, it is required that the investigator and institution permit authorized representatives of the company, of the regulatory agency(s), and the IEC/IRB direct access to review the patient's original medical records for verification of study-related procedures and data. Direct access includes examining, analyzing, verifying, and reproducing any records and reports that are important to the evaluation of the study. The investigator is obligated to inform and obtain the consent of the patient to permit named representatives to have access to his/her study-related records without violating the confidentiality of the patient.

